## 2 STUDY DESCRIPTION

### 2.1 Study Design

The study design schematic is presented in [Figure 2.1-1](#).

**Figure 2.1-1: Study Design Schematic**

This is a phase 3, randomized, double-blind, multicenter trial of adjuvant nivolumab versus placebo in adult male or female subjects who have undergone radical resection of IUC originating in the bladder or upper urinary tract (renal pelvis or ureter) and are at high risk of recurrence:

- Subjects who received neo-adjuvant cisplatin chemotherapy: ypT2-pT4a or ypN+
- Subjects who have not received neo-adjuvant cisplatin chemotherapy: pT3-pT4a or pN+ and are not eligible for or refusing adjuvant cisplatin chemotherapy

Approximately 700 subjects will be randomized in a blinded fashion 1:1 to nivolumab versus placebo within 120 days of radical resection and stratified by nodal status (N+ vs. N0/x with < 10 nodes removed vs. N0 with  $\geq 10$  nodes removed), tumor PD-L1 expression ( $\geq 1\%$ , < 1% / indeterminate), and use of cisplatin neo-adjuvant chemotherapy.

Treatment, in the absence of prohibitive toxicities, disease recurrence/progression, or withdrawal of consent will be continued for a maximum of 1 year. The co-primary endpoint is DFS in subjects with tumors expressing PD-L1 at  $\geq 1\%$  (2.5% alpha) and in all randomized subjects (2.5% alpha). The overall sample size is set up to allow a clinically meaningful effect to be statistically significant at alpha level of 2.5% (two-sided) in the all randomized group.

Even weighting of the alpha distribution between DFS assessment in all randomized (N = 700) and PD-L1 expressers (~ 42% of the all randomized population) reflects an assumption of enrichment of nivolumab efficacy in the PD-L1 expressers.

At the time of the revised protocol 03, the anticipated prevalence of PD-L1 expression  $\geq 1\%$  was 46% (original study design anticipated 50% prevalence) and the PD-L1 expression < 1% population in the study was capped at 54%.

During the execution of the study the PD-L1 at  $\geq 1\%$  rate was  $\approx 42\%$ , for this reason in revised protocol 04 the cap was removed to make the study sample representative of the study population.

Hence, it is anticipated that the final population will include approximately 42% of patients who are PD-L1 expression  $\geq$  1%.

The number of randomized subjects with upper tract urothelial cancers (UTUC) is capped at approximately 20% (140 subjects) of total global enrollment. Once approximately 140 subjects with UTUC are randomized, only subjects with bladder cancer are enrolled.

Following discontinuation of study therapy, subjects will be followed for survival and those that have not had a non-urothelial tract recurrence will be followed for recurrence.

## 2.2 Treatment Assignment

After informed consent has been obtained and the subject's eligibility is established, the subject will be enrolled and a number will be assigned through an interactive voice response system (IVRS). Subjects will be randomized in a 1:1 ratio to Arm A (nivolumab) or Arm B (placebo) stratified by the following factors:

- PD-L1 expression level ( $\geq$  1% vs. < 1%/indeterminate)
- Receipt of neo-adjuvant cisplatin based chemotherapy for IUC (Yes/No)
- Pathologic status of disease in lymph nodes (N+ vs. N0/x with < 10 nodes removed vs. N0 with  $\geq$  10 nodes removed)

## 2.3 Blinding and Unblinding

The Sponsor, subjects, investigator and site staff will be blinded to the study therapy administered. Each investigative site must assign an unblinded pharmacist/designee, and an unblinded site monitor will be assigned to provide oversight of drug supply and other unblinded study documentation.

## 2.4 Protocol Amendments

This SAP incorporates the following amendments:

**Table 2.4-1: Protocol Amendments**

Amendments	Date of Issue	Summary of Major Changes
Revised Protocol 1	21-OCT-2015	Modified randomization rate from 2:1 to 1:1; increased total number of treated subjects from 600 to 640; other minor changes, including simplifying the description of the study population and definition of recurrences
Revised Protocol 2	18-AUG-2016	Extends acceptable period of time between radical resection and randomization from 90 days to 120 days; clarifies pathology language for eligibility; clarifies recurrence language, updates safety and contraceptive language to be consistent with nivolumab Investigators Brochure version 15; other minor changes.
Revised Protocol 3	18-JUL-2017	Provides a more precise description of low- and high-risk non-muscle invasive bladder cancer (NMIBC) conforming to nomenclature used in the 1973 WHO and 2004 WHO/ISUP guidelines; aligns the synopsis with the body of the protocol with respect to non-eligibility of subjects with high-

**Table 2.4-1: Protocol Amendments**

Amendments	Date of Issue	Summary of Major Changes
		risk NMIBC; states that subjects with CIS at urethral or ureteral surgical margins are not eligible for study; changes the PD-L1 expression $\geq 1\%$ from 50% to 46% in accord with recently published data from the CA209-275 registrational study; applies a 20% cap on the number of pelvis and ureter cancer subjects randomized to the study; states that suspect lesions observed during screening procedures must be discussed with the MM prior to randomization; other minor changes.
Revised Protocol 4	19-DEC-2018	Incorporates statistical modifications (including sample size increases from 640 to 700), removal of the cap on PD-L1 $< 1\%$ , and adds PFS2 as exploratory endpoint. Revisions to Inclusion and Exclusion Criteria; and timing of TSH laboratory tests. Updates to the most recent guidance for nivolumab treatment. Minor formatting and typographical corrections were corrected.
Revised Protocol 5	XX-SEP-2019	Addition of a formal interim OS analysis at the time of final DFS analysis for both study populations (PDL1 $\geq 1\%$ and all randomized subjects).

## 2.5 Data Monitoring and Other External Committees

A Data Monitoring Committee (DMC) will be established to provide oversight of safety and efficacy considerations in protocol CA209274. Additionally, the DMC will provide advice to the sponsor regarding actions the committee deems necessary for the continuing protection of subjects enrolled in the study. The DMC will be charged with assessing such actions in light of an acceptable benefit/risk profile for nivolumab. The DMC will act in an advisory capacity to BMS and will monitor subject safety and evaluate the available efficacy data for the study. The oncology therapeutic area of BMS has primary responsibility for design and conduct of the study.

## 3 OBJECTIVES

### 3.1 Co-Primary Objectives

- To compare the DFS for nivolumab versus placebo in all randomized subjects
- To compare the DFS for nivolumab versus placebo in subjects with tumors expressing PD-L1 ( $\geq 1\%$  membranous staining in tumor cells)

### 3.2 Secondary Objectives

- To compare overall survival (OS) for nivolumab versus placebo in subjects with tumors expressing PD-L1 ( $\geq 1\%$  membranous staining in tumor cells) and all randomized subjects
- To evaluate non-urothelial tract recurrence free survival (NUTRFS) for nivolumab versus placebo in subjects with tumors expressing PD-L1 ( $\geq 1\%$  membranous staining in tumor cells) and all randomized subjects

## 4 ENDPOINTS

### 4.1 Efficacy Endpoints

#### 4.1.1 *Disease-Free Survival*

Disease-Free Survival is the primary endpoint of the study and will be programmatically determined based on the disease recurrence date provided by the investigator.

The following recurrence types are included in the DFS endpoint:

- Local, urothelial tract: any high- and intermediate-risk NMIBC and any new invasive urothelial carcinoma in the lower or upper urothelial tract (defined as T2 or greater), including lesions thought to be a second urothelial carcinoma primary
- Local, non-urothelial tract: Any recurrence in pelvic soft tissue or involving pelvic nodes below the aortic bifurcation
- Distant: Any non-local recurrence

Low-risk NMIBC will **not** be reported as a recurrence event for the DFS endpoint.

Subjects who die without a reported recurrence will be considered to have recurred on the date of their death.

DFS rate at time  $T$  (e.g. 6 months, depending on the minimum follow-up) is defined as the probability that a subject has no disease recurrence and is alive at time  $T$  following randomization, based on the Kaplan-Meier estimate.

The first on-study non-cystoscopy tumor assessment is scheduled to be conducted at 12 weeks ( $\pm 1$  week) from the date of first dose. Subsequent non-cystoscopy tumor assessments are scheduled every 12 weeks ( $\pm 1$  week) up to Week 96, then every 16 weeks ( $\pm 2$  weeks) up to Week 160, then every 24 weeks ( $\pm 4$  weeks) until non-urothelial tract recurrence or treatment is discontinued (whichever occurs later) for a maximum of 5 years.

[figure not shown]
Cystoscopy in subjects with upper GU primaries who still have bladder intact will occur in addition to other tumor imaging assessments every 12 weeks ( $\pm 1$  week) from the date of first dose to Week 48, then every 24 weeks ( $\pm 2$  weeks) up to Week 96, then every 48 weeks ( $\pm 4$  weeks) until non-urothelial tract recurrence or treatment is discontinued (whichever occurs later) for a maximum of 5 years.

The **primary definition of DFS (DFS truncated at subsequent therapy and new non-urothelial carcinoma primary cancer)** is defined as the time between the date of randomization and the date of first documented recurrence (local urothelial tract, local non urothelial tract or distant), or death due to any cause, whichever occurs first. The primary definition of DFS accounts for subsequent anticancer therapy (see [Table 4.1.1-11b\)](#)) and new non-urothelial carcinoma primary cancer by censoring at the last evaluable disease assessment on or prior to the date of subsequent therapy/new non-urothelial carcinoma primary cancer.

Detailed censoring rules for the primary definition of DFS are presented in Figure 4.1.1-1 and Table 4.1.1-1.

The secondary definition of DFS accounts for disease assessments occurring on or after initiation of subsequent anticancer therapy. Censoring scheme will be the same as for the primary DFS definition except that new anticancer therapy censoring that will be ignored in this sensitivity analysis. The secondary definition of DFS accounts for new non-urothelial carcinoma primary cancer by censoring at the last evaluable disease assessment on or prior to the date of new non-urothelial carcinoma primary cancer.

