3.3.2 Exclusion Criteria

1) Target Disease Exceptions

- a) Partial cystectomy in the setting of bladder cancer primary tumor or partial nephrectomy in the setting of renal pelvis primary tumor.
- b) Adjuvant systemic or radiation therapy for urothelial or prostatic carcinoma following radical surgical resection of urothelial carcinoma.

2) Medical History and Concurrent Diseases.

- a) Any serious or uncontrolled medical disorder that, in the opinion of the investigator, may increase the risk associated with study participation or study drug administration, impair the ability of the subject to receive protocol therapy, or interfere with the interpretation of study results.
- b) Prior malignancy active within the previous 3 years except for locally curable cancers that have been apparently cured, such as basal or squamous cell skin cancer, prostate cancer with evidence of undetectable Prostate Specific Antigen (PSA) or carcinoma in situ of the prostate, cervix or breast. Patients with known history of recent metastatic urothelial carcinoma will be excluded.
- c) Subjects with active, known or suspected autoimmune disease. Subjects with vitiligo, type I diabetes mellitus, residual hypothyroidism due to autoimmune condition only requiring hormone replacement, psoriasis not requiring systemic treatment, or conditions not expected to recur in the absence of an external trigger are permitted to enroll.
- d) Subjects with a condition requiring systemic treatment with either corticosteroids (> 10 mg daily prednisone equivalents) or other immunosuppressive medications within 14 days of study drug administration. Inhaled or topical steroids and adrenal replacement doses > 10 mg daily prednisone equivalents are permitted in the absence of active autoimmune disease.
- e) Subjects with history of life-threatening toxicity related to prior immune therapy (eg. anti-CTLA-4 or anti-PD-1/PD-L1 treatment or any other antibody or drug specifically targeting T-cell co-stimulation or immune checkpoint pathways) except those that are unlikely to re-occur with standard countermeasures (eg. hormone replacement after adrenal crisis).

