**Table 4.1.1-1: Censoring Scheme used in Primary Definition of DFS**

Situation	Date of Progression or Censoring	Outcome
Death from any cause without recurrence and no new anticancer therapy started 1)b) nor new non-urothelial carcinoma primary cancer	Date of death	DFS event
New anticancer therapy 1)b) received without recurrence reported prior to or on the same day	Date of last evaluable disease assessment prior to or on the same date of initiation of subsequent therapy	Censored
New non-urothelial carcinoma primary cancer without urothelial carcinoma recurrence reported prior to or on the same day	Date of last evaluable disease assessment prior to or on the same date of diagnosis of new non-urothelial carcinoma primary cancer	Censored

a) Disease assessments and death if any, occurring after start of subsequent anti-cancer therapy or after new non-urothelial carcinoma primary cancer are not considered.

b) New anticancer therapy includes systemic therapy, tumor directed radiotherapy and tumor directed surgery (**except TURBT**). As per protocol, the only exception is that a single dose of intravesical chemotherapy instilled immediately after resection of low-risk NMIBC (not considered as a DFS event), is permitted. Therefore **any use of one single dose of chemotherapy given via intravesical route should NOT be considered as subsequent treatment**.

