#### 4.1.2 Overall Survival

Overall survival (OS) is key secondary endpoint and defined as the time from randomization to the date of death from any cause. For subjects that are alive, their survival time will be censored at the date of last contact date (or “last known alive date”). OS will be censored at the date of randomization for subjects who were randomized but had no follow-up.

Survival follow-up will be conducted every 3 months after subject’s off-treatment date.

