#### **7.5.1.1 Analysis of Disease-Free Survival**

In case of formal comparison (interim or final), DFS will be compared between the treatment groups via stratified log-rank test in the appropriate co-primary population at an overall two-sided  $\alpha = 0.025$  level for each co-primary population. The stratification factors are summarized in the [section 7.5](#).

An O'Brien and Fleming  $\alpha$ -spending function will be employed to determine the nominal significance levels for the interim and final analyses. The estimate of the DFS hazard ratio between treatment groups will be calculated using a stratified Cox proportional hazards model, with treatment as the sole covariate. Ties will be handled using the exact method. A two-sided (1-adjusted  $\alpha$ )% CI (adjusted for interim) for the hazard ratio will also be presented.

The DFS function for each treatment group will be estimated using the KM product limit method and will be displayed graphically. A two-sided 95% CI for median DFS in each treatment group will be computed via the log-log transformation method. DFS rates at fixed time points (e.g. 6 months, depending on the minimum follow-up) will be presented along with their associated 95% CIs. These estimates will be derived from the Kaplan Meier estimate and corresponding CIs will be derived based on Greenwood formula for variance derivation and on log-log transformation applied on the survivor function.

The primary definition of DFS adjusting for subsequent anticancer therapy will be used in this analysis. The two-sided log-rank p-value will be reported.

The source of DFS event (recurrence or death) will be summarized by treatment group. The status of subjects who are censored (as per primary definition of DFS) in the DFS KM analysis will be tabulated for each treatment group including the following categories:

- On-study (on-treatment, in follow-up)
- Off-study (lost to follow-up, withdraw consent, never treated)
- No baseline disease assessment
- No on-study disease assessment and no death
- Received subsequent anticancer therapy
- New non-urothelial carcinoma primary cancer

A by-subject listing will be presented including treatment group, DFS duration under the primary definition, whether the subject was censored under the primary definition, and if censored, the reason.

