### **7.5.1.2 Supportive Analyses of Disease-Free Survival**

The following sensitivity analyses will be conducted using the primary and secondary definition of DFS:

- 1) DFS using stratification factors as obtained from the baseline CRF pages (instead of IRT). The hazard ratio associated with treatment will be presented along with the associated two-sided 95% CIs. This analysis will be performed only if at least one stratification variable/factor at randomization (as per IRT) and baseline are not concordant for at least 10% of the randomized subjects.
- 2) DFS using an unstratified log rank test. The hazard ratio associated with treatment will be presented along with the associated two-sided 95% CIs.
- 3) A multivariate Cox regression model will be used in order to estimate the treatment effect after adjustment for possible imbalances in known or potential prognostic factors. The factors used in the randomization, which, by definition, will be balanced across treatment groups, will still be included in the model as stratification factors. However, all additional factors will be incorporated as covariates. The additional factors, which are all measured at baseline, will include:
  - Age (< 65 vs. ≥ 65 year)
  - Gender (Male vs. Female)
  - Baseline ECOG status (0 vs. 1 vs. 2)
  - Pathological status (pT0-2 vs. pT3 vs. pT4)

The level of the covariate normally associated with the worst prognosis will be coded as the reference level. The hazard ratio associated with treatment and with each of the baseline covariates will be presented along with associated 95% CIs.

- 4) DFS for subjects with no relevant protocol deviations. This analysis will be conducted only if there are more than 10% subjects with relevant protocol deviations. The hazard ratio associated with treatment will be presented along with the associated two-sided 95% CIs.
- 5) DFS accounting for missing disease assessments prior to DFS event (recurrence or death). This analysis will be performed only if at least 10% of DFS events (in the population of interest) have two or more missing prior disease assessment (no protocol specified disease assessment imaging completed at the expected timepoint). It will apply the following restriction to the primary definition in case a subject has two or more missing disease assessments, the subject will be censored at the last disease assessment date prior to DFS event.

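### Does DFS need a supportive analysis that lifts the censoring at a new non-urothelial cancer?

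*SAP*

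**What the plan says.** SAP 4.1.1 names the primary definition for what it does: "DFS truncated at subsequent therapy and new non-urothelial carcinoma primary cancer". Footnote a to SAP Table 4.1.1-1 spells out the consequence: "Disease assessments and death if any, occurring after start of subsequent anti-cancer therapy or after new non-urothelial carcinoma primary cancer are not considered". Protocol Table 8.3.1-1 has a matching censoring row for a second non-urothelial primary.

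The secondary definition drops the censoring at new anticancer therapy but keeps the other rule: "The secondary definition of DFS accounts for new non-urothelial carcinoma primary cancer by censoring at the last evaluable disease assessment".

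SAP 7.5.1.2 then limits the robustness work to these two definitions: "The following sensitivity analyses will be conducted using the primary and secondary definition of DFS".

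Two other parts bear on the point. SAP 7.5.1.1 tabulates censored subjects by arm and reason, with "New non-urothelial carcinoma primary cancer" as its own category, and lists the reason subject by subject. Overall survival (OS), in SAP 4.1.2, is "defined as the time from randomization to the date of death from any cause", so it keeps every later death.

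**The concern.** DFS is described as recurrence or death from any cause. Yet a subject who develops, say, a lung cancer leaves the analysis at the last scan before that diagnosis, and a later death or urothelial recurrence is not counted. A new cancer can raise the risk of death, so this censoring may be informative. If incidence also differed between arms, the HR could be biased in either direction.

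The SAP varies one of its two truncation rules (new therapy) and leaves the other fixed. A reader of the final report could see how often the second rule applied, but not what it did to the HR of a co-primary endpoint.

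**Working it through.** **1. Which analysis lifts which rule**

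| DFS analysis | Censor at new therapy | Censor at new non-urothelial cancer |
|---|---|---|
| Primary definition | yes | yes |
| Secondary definition | no | yes |
| Seven supportive analyses (7.5.1.2) | as primary or secondary | yes |

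The seven are CRF strata, unstratified test, multivariate Cox, no relevant deviations, missing assessments, weighted log-rank with HR before and after 6 months, and the proportional-hazards check. The missing-assessment analysis only adds censoring. The textual claim therefore holds for the visible text.

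**2. Reproducing the plan's figures**

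Inputs from SAP 5: control S(t) = 0.32 + 0.68·exp(-0.11t), with t in months; nivolumab plateau 0.47 (0.54 in PD-L1 ≥ 1%) after a 3-month delay; 700 subjects at 16 per month, so 700/16 = 43.75 months of accrual; data cut at month 60.

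- Control median: ln(0.68/0.18)/0.11 = 12.1 months (plan 12).
- At month 3: S(3) = 0.32 + 0.68·exp(-0.33) = 0.809. Nivolumab thereafter: 0.47 + (0.809 - 0.47)·exp(-0.11(t - 3)), with 0.54 in place of 0.47 for PD-L1 ≥ 1%.
- Expected events and average HR: 409.6 and 0.714 (plan 410 and 0.72); in PD-L1 ≥ 1%, 162.2 and 0.600 (plan 162 and 0.61).
- Power, Φ(√d/2·|ln HR| - 2.241): for d = 410 and HR 0.72, Φ(3.326 - 2.241) = 86% (plan 87%); for d = 162 and HR 0.61, Φ(3.146 - 2.241) = 82% (plan 80%).

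**3. Adding a second cancer**

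Assumed, because the documents give no figures: incidence r of 1% to 4% per year, and excess death hazard h of 0, 0.2 or 0.5 per year after the second cancer. At equal rates, about 12 to 44 subjects (5 to 20 with PD-L1 ≥ 1%) reach this censoring by month 60. The Cox HR is computed with follow-up ending at the second cancer (the rule) and with follow-up continuing to the data cut (all events). Shift = HR with all events minus HR under the rule.

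| Scenario | Shift, all randomized | Shift, PD-L1 ≥ 1% |
|---|---|---|
| Equal rates 1–4%, h = 0 | -0.001 to -0.004 | -0.001 to -0.005 |
| Equal rates 1–4%, h = 0.2–0.5 | +0.001 to +0.009 | +0.001 to +0.014 |
| 1% placebo, 3% nivolumab, h = 0.2–0.5 | +0.011 to +0.023 | +0.012 to +0.025 |
| 3% placebo, 1% nivolumab, h = 0.2–0.5 | -0.008 to -0.013 | -0.007 to -0.010 |

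The model censors at diagnosis and is unstratified. Censoring at the last scheduled scan instead changes the largest shifts from 0.023 and 0.025 to 0.021 and 0.024.

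**4. Against sampling error**

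SE of log HR is about 2/√410 = 0.099 and 2/√162 = 0.157. Largest case, all randomized: ln(0.7383/0.7154) = 0.0315, and 0.0315/0.099 = 0.32 SE. PD-L1 ≥ 1%: ln(0.6272/0.6024) = 0.0403, and 0.0403/0.157 = 0.26 SE. With equal rates the shift is at most 0.14 SE.

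**5. The definition that is formally tested**

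The shifts in step 3 describe the secondary definition. The formal test uses the primary one, which also censors at new treatment: "New anticancer therapy includes systemic therapy, tumor directed radiotherapy and tumor directed surgery". Many subjects with a new cancer would be censored on that ground anyway. If a share q starts therapy at diagnosis, the largest shift in step 3 becomes:

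- q = 0.5: 0.012 (PD-L1 ≥ 1%: 0.013)
- q = 0.8: 0.005 (0.005)

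If nobody starts therapy (q = 0), the step 3 figures apply unchanged.

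**The case for a change.** The strongest case for acting is that the analysis is cheap and fits the SAP's own logic. One of two named truncation rules is tested and the other is not. Tumor assessments continue after dosing stops (Protocol 4.5.5), and deaths are followed for OS, so little or no new data would be needed. Specifying the analysis now would avoid a post hoc choice if the counts proved unequal. The planned table shows frequency only, and OS omits urothelial recurrences. Blinding and a common imaging schedule limit differential detection but cannot exclude a true difference in incidence.

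All of this stands as description, but it does not establish a gain:

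- The proposal would leave the primary and secondary analyses as they are, and the added analysis would carry no alpha.
- Eligibility already limits the problem by excluding "Prior malignancy active within the previous 3 years except for locally curable cancers that have been apparently cured". The censoring rule also covers cancers of the locally curable kind, for which an excess death hazard of 0.2 to 0.5 per year is harsh.
- The natural version, which lifts both rules and is compared with the secondary definition, would isolate the effect on the secondary HR and not on the tested one.
- Counting events after a second cancer has its own bias. Deaths from unrelated cancers enter, scans may become less complete, and new lesions must be attributed to one cancer or the other. Protocol 5.4.3 does not require histology when recurrence is unequivocal, so metastases of the second cancer could be recorded as urothelial recurrence. That is a plausible reason to censor there.

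**Conclusion.** No change is needed. The gap is real in the text, but the rule is prespecified, visible in the name of the endpoint definition and consistent between protocol and SAP. The by-arm table and the subject listing in SAP 7.5.1.1 will show whether these cases are few or unbalanced. If they are unbalanced, analysts can run the extra comparison then: SAP 9 describes the listed analyses as potential content of the report and does not present them as a closed set.

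Under the assumed rates, equal incidence moves the HR by between -0.005 and +0.014. The extreme case gives about 0.025, or 0.013 under the tested definition if half of these subjects start therapy at diagnosis. These sizes rest on assumed second-cancer rates, excess death hazards and therapy shares, none of which the documents supply. They are illustrations of scale only. The conclusion covers the visible SAP text; some other sections are redacted.
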